4.3 EXPLORATORY OBJECTIVES

- The potential of nalbuphine HCl ER tablets to impact on the measurement of nerve fiber density (histology) and MOR/KOR density (histology, Western Blot) and Histological (H&E) changes in skin biopsies taken Baseline and the final Treatment

Period Visit to investigate possible correlation with any clinical response and also compared to biopsy material assessed during study TR03 (optional period at select sites only).

5 STUDY ENDPOINTS

5.1 PRIMARY ENDPOINT

- A description of the incidence and nature of TEAEs during Treatment Weeks 5-50

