Safety Assessments	
Safety will be assessed based on adverse events (AEs), clinical laboratory measurements, Investigator review and central cardiac core laboratory read-12-lead electrocardiogram (ECG), vital signs and physical examinations.
 
An unblinded, independent Data Safety Monitoring Board (DSMB) will periodically review safety data. The frequency of data review and DSMB processes are outlined in the DSMB charter.

Efficacy Assessments	
Efficacy Measurements:
 
 • Worst itch intensity (from NRS) • Average itch intensity (from NRS) • VRS (itchy, burning and stinging) • ItchyQoL • MOS Sleep-R • HADS • PAS • PBI-P • Frequency, pattern, and reasons for dose titration • Use of rescue medications for itching 
At selected sites (optional procedures):
 
 • Nerve fiber density (histology) at Baseline and the final Treatment Period Visit • MOR/KOR density (histology, Western Blot) at Baseline and the final Treatment Period Visit • Histological analysis (H&E) at Baseline and the final Treatment Period Visit
Pharmacokinetic Assessments	
Blood samples for nalbuphine plasma concentration (and metabolites as needed) will be collected periodically according to the Schedule of Events (Appendix 1).

Study Endpoints	
Primary Endpoint:
 
 • A description of the incidence and nature of TEAEs during Treatment Weeks 5- 50 
Secondary Endpoints
 
Visit 1a or 1b will serve as the baseline visit for efficacy endpoints. Visit 1a will be the baseline for patients directly entering the Treatment Period as of Visit 1a. Visit 1b will be the baseline for patients entering the

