In healthy subjects, the dosing regimen resulted in mainly Grade 1 AEs and the dose escalation was tolerable in 8/9 subjects dosed. Of the nine healthy subjects enrolled, one subject withdrew from the study secondary to AE Grade 1 level gastrointestinal reflux, nausea/vomiting and vertigo symptoms at the 120 mg BD dosing level. The subject recovered from the AE following drug discontinuation. AEs that occurred in greater than two subjects were somnolence (N=2), headaches (N=2), flatulence (N=2) and constipation (N=3).

In the HD subjects, there were no deaths or drug-related serious AEs. There were no dose-limiting AEs reported as defined as two HD subjects experiencing a drug-related AE of Grade 3. A total of 72 AEs were reported in the 15 HD subjects of Cohort 1. The nervous and gastrointestinal organ systems had the highest incidence of AEs. The most frequently occurring AEs were nausea and somnolence. Of the 13 HD subjects who completed the study (10 HD patients assigned to dose up to 180 mg BID and 3 HD subjects assigned to dose up to 240 mg BID), 12 subjects completed the trial per protocol and 1 subject completed the study but did not dose titrate beyond 120 mg BID.

With regard to the gastrointestinal organ system, of the 14 HD subjects who completed 13 days of dosing (1 subject at 120 mg BID and 13 subjects at 180 mg BID), 4/14 (29%) experienced no nausea during the study and 7/14 (50%) experienced Grade 1 intensity nausea that was self-limited and only occurred at the initiation dose of 30 mg. One subject (1/14, 7%) experienced Grade 2 nausea starting from the 60 mg BID through the 180 mg BID dose. Three subjects (3/14, 21%) only developed nausea at the 180 mg dose level.

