3.3.3 Additional Nalbuphine HCl ER Tablet Clinical Data

In addition to the subjects in the TR01 study, a total of 331 subjects have been exposed to nalbuphine HCl during the course of 8 previous clinical studies.

Four Phase 1 studies were early biopharmaceuticals studies conducted in healthy subjects mainly for formulation selection and as such they support the safety of the drug product. In addition, two Phase 1 studies were conducted with the current clinical formulations and each consisted of a single dose study assessing the safety, tolerability, and PK of the current tablet formulations in the 30 mg -180 mg range.

A safety and efficacy analgesic study was conducted in subjects with dental-pain following third molar extractions following a single dose (placebo or 60 mg or 120 mg). The subjects were otherwise healthy male and female subjects. The study also contained PK-PD analysis demonstrating an analgesic dose-response relationship, with clear differentiation between the nalbuphine dose groups and placebo group.

Oxygen saturation was monitored via pulse oximetry as a safety precaution during Phase 1 studies and in the single dose third molar extraction dental pain treatment study. All subjects who received the drug had oxygen saturation levels within the 90%-100% range during the studies.

A safety and efficacy analgesic study was conducted in a patient population experiencing osteoarthritic related joint pain using the current nalbuphine HCl ER 60 mg tablet. The population was demographically older with the mean age of 57 years and a range extending from age 40-70 years. Subjects were dosed continuously for up to 3 weeks starting at 60 mg BID up to a dose of 180 mg BID. Subjects who tolerated the initial dosing were titrated up in weekly increments of 60 mg BID to the maximal dose of 180 mg BID. The AEs that developed mainly had their onset at the initiation of dosing with no new type of AE developing in any statistically significant incidence during the course of dose escalation.

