4 STUDY OBJECTIVES

4.1 PRIMARY OBJECTIVE

The primary objective of the study is:

- To evaluate the safety and tolerability of nalbuphine HCl ER tablets during a drug treatment period of up to 50 weeks.

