In order to facilitate analysis of the clinical safety data and efficacy data, patients in the present study will begin titration at the 30 mg QD dose and titrate to only a maintenance dose ranging between 30 mg BID and 180 mg BID. The 30 mg BID and 60 mg BID doses are believed to be only marginally effective doses based on available TR01 data. However there is a two time dose reduction permitted for all subjects during Treatment Weeks 5-50 (see [Table 3](#)) to the next lower allowed dose (e.g., a subject at the 90 mg BID maintenance dose will be permitted a dose reduction to 60 mg BID or subsequently to 30 mg BID and then be maintained at that dose level for the remainder of the study).

The study population being evaluated is an intended target population for oral nalbuphine HCl ER tablets: prurigo nodularis patients.

Patients will be closely monitored for safety. All patients will be seen at the Investigator site (See [Schedule of Events in Appendix 1](#)). Adverse events and vital signs will be recorded. Additionally, 12-lead ECGs (locally and centrally read), physical examinations, and clinical laboratory testing will be conducted to monitor safety on patients receiving study drug. Safety monitoring will be done to address the primary objective of evaluating the longer term safety of study drug exposure. The primary endpoint is a description of adverse events during up to 50-weeks of treatment with nalbuphine HCl ER tablets. An important secondary endpoint objective of the study is to use recorded PAS metrics to assess the study drug anti-pruritic suppression of the scratching behavior of the subject and impact on skin lesion improvement. Changes in patient-reported outcome measures: Worst itch NRS, Average itch intensity NRS, VRS (itchy, burning and stinging), ItchyQoL, MOS Sleep-R, HADS and PBI-P will be explored.

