To mitigate opioid-related side effects, nalbuphine will be titrated over 4 weeks based on tolerability to a dose that is between 30 mg BID to 180 mg BID (see [Table 3](#)). Titration is a clinical management strategy consistent with dosing of opioids in general (Jovey 2003). The titration regimen planned in this study is similar to the regimen used in study TR01, in which doses in the planned range were well tolerated ([Section 3.3.2](#)) except uptitration is not a forced titration. This will provide flexibility for each patient to assess tolerability. In this study, the combination of a low starting dosing (30 mg on the first day) followed by a relatively slow titration (dose escalation after a minimum of six consecutive doses over approximately 3 days) is expected to minimize treatment-limiting opioid adverse effects. See [Table 3](#) for the drug titration scheme. The time interval between dose escalations is consistent with the "three day tolerance check" suggested by the National Opioid Use Guideline Group of Canada (2010) for outpatient clinical practice management of opioid drug titration as part of monitoring patient side effects.

Nalbuphine has μ -opioid antagonist pharmacological properties. To minimize the possibility of acute opiate withdrawal occurring at drug initiation in a physically dependent subject, patients receiving daily doses of opiates are excluded from the study. Patients who require ongoing non-daily opiates concurrently with nalbuphine should be monitored carefully for additive opiate effects. If patients develop a new need for daily opiates during the study, the Investigator is required to contact the Medical Monitor to discuss the specifics of the situation.

It is known from prior studies, that gastrointestinal opioid-like adverse effects (e.g., nausea, vomiting, and constipation) occur early and can be treatment-limiting. In anticipation of the possible occurrence of these effects, pre-medications for nausea will be permitted and Investigators will be advised to use pharmacologic or non-pharmacologic means to avoid constipation as clinically indicated. In anticipation of the possible occurrence of central nervous system (CNS) AEs such as somnolence, patients will be instructed to be aware of possible CNS AEs that may occur. The evening doses during the Titration Period should

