9.6.2 Treatment Period (Treatment Weeks 1-50)

Patients who enter the Treatment Period on Visit 1a will be in the Treatment Period for up to 50 weeks and thus are eligible to receive study drug for up to 50 weeks.

Patients who enter the Treatment Period from the Observation Period will be in the Treatment Period for up to 46 Treatment Weeks. Patients enter the Treatment Period from an Observation Visit (OV) when their Worst itch NRS is greater than or equal to 5 (≥ 5).

Regardless of how many treatment weeks the patient was on study drug, all patients who enter the Treatment Period will complete End of Treatment Visit TV14. Since all patients must titrate to their maintenance dose over the first four weeks of the Treatment Period, Visits 1a/Visits 1b (TV 1) and TV 2 over the first four weeks of the Treatment Period will be common to all subjects in TR03ext regardless of when they enter into the Treatment Period. Patients who transition from the Observation Period to the Treatment Period at a respective Observation Visit will follow the Treatment Visit schedule outlined in [Table 8](#).

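### Version 2.0 limits its primary endpoint to Treatment Weeks 5-50 in Section 5.1, but Section 9.2 and the primary objective cover all treatment, so titration falls outside the primary safety result

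*Protocol*

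**What the plan says.** All references are to protocol Version 2.0 unless stated.

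- **Primary endpoint, Section 5.1:** "A description of the incidence and nature of TEAEs during Treatment Weeks 5-50". The synopsis repeats it: "A description of the incidence and nature of TEAEs during Treatment Weeks 5- 50".
- **Primary endpoint, as described in Section 9.2:** "The primary endpoint is a description of adverse events during up to 50-weeks of treatment with nalbuphine HCl ER tablets". No week is excluded.
- **Primary objective, Section 4.1:** "To evaluate the safety and tolerability of nalbuphine HCl ER tablets during a drug treatment period of up to 50 weeks".
- **Titration, Section 9.6.2:** "all patients must titrate to their maintenance dose over the first four weeks of the Treatment Period". Table 3 allows at most 60, 120 and 180 mg BID at the end of Treatment Weeks 1, 2 and 3. In Week 4 the dose is only held or reduced.
- **Stopping for intolerance:** Sections 9.6.2.1.1 to 9.6.2.1.3 take patients off drug for intolerability at the Week 2 call, the Week 3 visit and the Week 4 call.
- **Timing of effects, Section 9.3:** gastrointestinal opioid-like effects "occur early and can be treatment-limiting". On the osteoarthritis study, Section 3.3.3 says: "The AEs that developed mainly had their onset at the initiation of dosing".

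Version 1.0 has the same pair of statements in its Sections 5.1 and 9.2, so the amendment did not introduce the difference. Neither version gives a reason for starting the endpoint at Week 5.

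**The concern.** This is a safety study with one primary endpoint, and the protocol states that endpoint in two ways. Someone working from Section 5.1 would report events in Weeks 5-50. Someone working from Section 9.2 would report events from the first dose. Only the second matches the primary objective, which covers tolerability as well as safety.

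The weeks in dispute are not arbitrary. They contain every first exposure to a higher dose, and also the scheduled contacts at which intolerant patients leave treatment before Week 5. Section 9.2 expects about one-third of entrants to come from the placebo arm of TR03, and their first exposure to nalbuphine falls in these weeks. A Weeks 5-50 result describes treatment after the dose has been adjusted to tolerance and some intolerant patients have stopped. On its own it does not answer the question in Section 4.1.

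**Working it through.** The documents give no sample size, power or other figure that depends on this window, so there is no stated number to reproduce. The check compares the windows, does the week arithmetic and recounts the prior data.

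**1. The windows**

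| Place (Version 2.0) | Window | Weeks 1-4 included? |
|---|---|---|
| Section 5.1, synopsis endpoint | Treatment Weeks 5-50 | No |
| Section 9.2 | Up to 50 weeks of treatment | Yes |
| Section 4.1 | Drug treatment period of up to 50 weeks | Yes |

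**2. Size of the gap in time**

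- Direct entrants: 50 − 46 = 4 weeks; 4/50 = 8.0% of treatment.
- Entrants from the Observation Period (up to 46 weeks, Section 9.6.2): 4/46 = 8.7%.
- Entrants after the full 12 observation weeks, with the combined limit of 50 weeks (Section 9.5): 50 − 12 = 38; 4/38 = 10.5%.

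The gap is a small share of time, but it is the whole of titration.

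**3. Early events in TR01 (Section 3.3.2, 14 hemodialysis subjects who completed 13 days of dosing)**

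- Any nausea: 14 − 4 = 10; 10/14 = 71%. Of these, "7/14 (50%) experienced Grade 1 intensity nausea that was self-limited and only occurred at the initiation dose of 30 mg".
- Any somnolence: 14 − 5 = 9; 9/14 = 64%. In 4/14 (29%) it occurred only at the 30 mg initiation dose.
- Caution: the printed nausea breakdown is 4 + 7 + 1 + 3 = 15 for 14 subjects, so these shares are indicative only.

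**4. What TR01 can and cannot show**

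Hemodialysis subjects were dosed for at most 15 days, and the osteoarthritis study for up to 3 weeks (Section 3.3.3). Both end before the equivalent of Treatment Week 5. They show that early events are common. They cannot show how many events begin later, so no split between Weeks 1-4 and Weeks 5-50 can be estimated from them.

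**5. Direction of the effect**

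On a fixed denominator of all treated patients, those with a TEAE in Weeks 5-50 are a subset of those with a TEAE in Weeks 1-50. The restricted incidence can only be equal or lower.

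An illustration, with assumptions that are not in the documents: 60 treated; 5% to 30% stop in Weeks 1-4, each with an event; of the rest, 30% have early events only and 20% have an onset in Weeks 5-50 (counts rounded).

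| Stop in Weeks 1-4 | Incidence, all treatment | Weeks 5-50, of all treated | Weeks 5-50, of those reaching Week 5 |
|---|---|---|---|
| 3 (5%) | (3+17+11)/60 = 52% | 11/60 = 18% | 11/57 = 19% |
| 6 (10%) | (6+16+11)/60 = 55% | 11/60 = 18% | 11/54 = 20% |
| 12 (20%) | (12+14+10)/60 = 60% | 10/60 = 17% | 10/48 = 21% |
| 18 (30%) | (18+13+8)/60 = 65% | 8/60 = 13% | 8/42 = 19% |

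The gap in this table comes from the assumed early share. It shows the mechanism and is not a forecast.

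**The case against.** The strongest reply is that little is lost. Adverse events are recorded at the two titration calls and at the Week 3 visit. The statistical methodology in the Version 2.0 synopsis summarises adverse event incidence with no Week 5 limit. Version 1.0 Section 19.9.2 summarises all treatment-emergent events after first dose; the Version 2.0 counterpart is listed in its contents, but its text lies beyond what is at hand. Reasons for titration changes and discontinuation are a secondary endpoint, a data safety monitoring board reviews safety, and nothing is tested. This stands: the window decides which result is called primary, not which data are reported.

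A maintenance-phase endpoint is also a reasonable choice. The dose is fixed at the end of Week 4 so that results can be read by achieved dose, and Section 9.2 stresses longer-term safety. That is fair as design, but the protocol does not say so, and Sections 4.1 and 9.2 say something else. Safety by maintenance dose is already a separate secondary objective.

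Section 9.3 also limits how far its warning carries. The remark about early, treatment-limiting effects concerns gastrointestinal effects in prior studies, and the same section expects the low start and slow titration to keep treatment-limiting effects to a minimum.

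A reader might infer from TR01 that none of the expected events would reach the Weeks 5-50 endpoint. The documents do not support this, because a study of at most 15 days cannot contain a later onset. A reader might also fault Section 5.1 for not saying whether an event that starts in Week 2 and persists past Week 5 is counted. That is a counting rule a protocol may leave to its statistical analysis plan.

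**Conclusion.** The inconsistency is real and in the current version. Section 5.1 and the synopsis restrict the primary endpoint to Weeks 5-50; Section 9.2 and the primary objective do not. As written in Section 5.1, the four titration weeks (8.0% of a 50-week course, up to 10.5% of a 38-week one) are outside the primary safety result, although the protocol itself places early effects and stops for intolerance there.

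The consequence is bounded. Titration events are absent from the primary answer but remain in the safety reporting; for Version 2.0 this rests on the synopsis and the schedule of assessments, since its Section 19 is not at hand. The effect on the headline incidence is downward or nil on an all-treated denominator, and its size cannot be derived from the documents. It would be too strong to say that titration safety goes unreported, or that the objective requires the primary endpoint to include washout: Section 4.1 speaks of the drug treatment period, and Table 2 lists washout separately.

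This should be fixed. In an uncontrolled, descriptive extension it does not invalidate the study.

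**What to change.** In Section 5.1 and the synopsis, define the primary endpoint as the incidence and nature of TEAEs from first dose through the end of treatment, presented by onset in Weeks 1-4 and Weeks 5-50. Show events with onset in washout separately, as supporting data. Use the same wording in Section 9.2. The maintenance result is then kept as its own column.

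If a maintenance-only endpoint is intended, restate Sections 4.1 and 9.2 to say so, give the reason for the Week 5 start, and report Weeks 1-4 TEAEs beside it.

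The cost is a wording change and one or two extra table columns, with no new data collection. The likely downside for the sponsor is a less favourable headline incidence.

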5.2 SECONDARY ENDPOINTS

Visit 1a or 1b will serve as the baseline visit for efficacy endpoints. Visit 1a will be the baseline for patients directly entering the Treatment Period as of Visit 1a. Visit 1b will be the baseline for patients entering the Treatment Period after participating in the Observation Period for any length of time.

- Assess skin lesion improvement using the metrics of the PAS
- Change from Baseline in Patient-Reported Outcome measures Worst itch NRS, average itch intensity NRS, VRS (itchy, burning and stinging), MOS Sleep-R, ItchyQoL, HADS) by Treatment Period study visit and Baseline NRS score
- Change between Baseline and the final Treatment Period visit in PBI-P
- A description of the percentage of patients utilizing various doses of nalbuphine HCl ER tablets by Study Week
- A description of the frequency and reasons for dose up- and down-titration and treatment discontinuation during the study
- Frequency and distribution by time on study of patients determined to meet failure-to-improve criteria
- Changes in the PRO measurements during the Washout Period after cessation of treatment of nalbuphine HCl ER tablets
- Time to first use of rescue medications and the number of days of use of rescue medications for itching
- To evaluate the daily changes in the Subjective Opiate Withdrawal Scale (SOWS) during the Washout Period after cessation of treatment of nalbuphine HCl ER tablets.

